**Figure 1 Study Schema**

AML = acute myeloid leukemia; BID = twice daily; CR = complete remission; HSCT = hematopoietic stem cell transplant; IV = intravenous; OS = overall survival; PO = orally; WT = wild type

Idasanutlin interferes with the binding of MDM2 to tumor protein -53 (TP53), thereby stabilizing p53 and allowing it to exert its anti-tumor activity. Because not all *TP53* mutations lead to a loss-of-function of the p53 protein, some patients with mutant *TP53* may still respond to treatment. The study will therefore allow enrolment of all patients irrespective of *TP53* mutation status. However, to best assess idasanutlin efficacy in AML, the primary analysis will be tested in *TP53* WT patients (see definition in section 4.1.1.1 and Appendix 2), representing about 85% of all patients enrolled. It is expected that about 15% of the enrolled patients in this study will carry a *TP53* mutation.

Prior to the final analysis, a non-binding interim analysis for futility is planned as well as a binding interim analysis for efficacy. Both interim analyses will be conducted by an iDMC (independent Data Monitoring Committee).

The futility interim analysis will be based on the endpoints of confirmed CR + CR with incomplete platelet recovery (CRp), event-free survival (EFS), and other safety data (see details of data monitoring in Section 3.2).

The interim analysis for efficacy on OS is planned at an information fraction of 80% OS events (220 OS events) in TP53 WT patients (see Section 4.11.3).

Accompanying this efficacy-interim-analysis, a non-binding futility assessment will be performed based on an OS hazard ratio (HR) greater than or equal to one.

With regard to study continuation on the basis of OS data at the interim efficacy analysis, a final OS analysis would occur at 275 OS events in TP53 WT patients and a follow up OS analysis will occur at end of study.

## **2.1 PROTOCOL SYNOPSIS**

The protocol synopsis is in

## **2.2 OUTCOME MEASURES**

### **2.2.1 Primary Efficacy Outcome Measures**

The primary endpoint for this study is OS in the TP53 WT population. OS is defined as the time from randomization to death from any cause. OS for patients who have not died at the time of the analysis will be censored at the last date the patient was known to be alive.

### **2.2.2 Secondary Efficacy Outcome Measures**

The secondary efficacy outcome measures for this study are as follows, for the TP53 WT population:

- CR is defined as a complete remission as reported by the investigator over the induction cycle (Cycle 1).
- EFS is defined as the time from the date of randomization to treatment failure (failure to achieve CR, set as day of final response assessment), relapse from CR, or death from any cause, whichever occurs first. Patients with no EFS event will be censored at the date of last response assessment (pre-HSCT) or last date known to be alive (post-HSCT). Patients with no EFS event and no post-baseline response assessment will be censored at date of randomization.
- Overall remission (ORR; CR, CRp, and complete remission with incomplete blood count recovery [CRi]) over the induction cycle (Cycle 1)
- DOR (or Duration of CR) is defined only for patients who achieve a CR and is measured from the date of achievement of CR until the date of relapse from CR, or death from any cause. Patients who do not have a DOR event will be

censored the date of last response assessment (pre-HSCT) or last known alive date (post-HSCT).

- The proportion of HSCT following a CR is defined as proportion of patients undergoing allogeneic HSCT following the corresponding CR
- CR in clinically actionable mutation defined subpopulations (FLT3, IDH1 and IDH2)
- OS in clinically actionable mutation defined subpopulations (FLT3, IDH1 and IDH2)

### **2.2.3 Safety Outcome Measures**

The safety and tolerability of idasanutlin + cytarabine in comparison with placebo + cytarabine will be assessed on both the *TP53* WT safety population and the all-patient safety population using the following safety outcome measures:

- Incidence, nature, severity, and seriousness of adverse events
- Incidence of clinically significant laboratory abnormalities
- Electrocardiograms (ECGs)
- Vital signs
- Death, including 30- and 60-day mortality rates

### **2.2.4 Exploratory Outcome Measures**

The pharmacodynamic (PD)/biomarker outcome measures for this study are as follows:

- PD biomarkers and other biomarkers (e.g., protein, nucleic acid, and other tumor cell-derived markers related to the mechanism of action of the study drug, which include, but are not limited to, markers of MDM2 or p53 pathway alterations) that may help predict patient subpopulations who are more likely to respond to the therapies in this study.
- Minimal residual disease (MRD)
  - Kinetics of MRD by flow cytometry and association of MRD response with outcomes
  - MRD by tracking AML-specific mutations and translocations and/ or expression of AML-related genes such as *Wilms tumor 1* [*WT1*])
- Prognostic value of disease related mutations
- Serum macrophage inhibitory cytokine-1 (MIC-1) profile (raw and/or adjusted from baseline as a percentage of change)
- 4-gene signatures by quantitative real-time polymerase chain reaction (qRT-PCR) as well as gene expression levels of the individual components of the signature (including MDM2)

- MDM2 protein expression measured by flow analysis

The efficacy exploratory Outcome Measures are as follows:

- Rate of CRMRD (CR without MRD as per European LeukemiaNet [ELN] guidelines [Dohner 2017] at a 0.1% cut-off for negativity as per ELN MRD working party consensus [Schoorhuis 2018]) within the ITT-all-patient and TP53 WT populations
- OS within the ITT-all-patient population
- Secondary efficacy endpoints within the ITT-all-patient population.
- CR during treatment: defined as complete remission as reported by the investigator at any time during treatment
- The proportion of HSCT as proportion of patients undergoing allogeneic HSCT regardless of response
- The proportion of HSCT following a CR/CRp/CRi is defined as proportion of patients undergoing allogeneic HSCT following the corresponding response (i.e. CR or CRp or CRi)
- Leukemia-free Survival (LFS, or duration of OR) is defined only for patients who achieve a remission (CR, CRp, or CRi) and is measured from the date of achievement of remission until the date of relapse from CR, CRp, CRi, or death from any cause. Patients who do not have an LFS event will be censored at the date of last response assessment.

### **2.2.5 Pharmacokinetic Outcome Measures**

The pharmacokinetic (PK) outcome measures for this study are as follows:

- Apparent clearance and apparent volume of distribution as well as the maximum concentration observed in plasma ( $C_{max}$ ), steady-state concentration at the end of a dosing interval (i.e., just prior to next drug administration [ $C_{trough}$ ]), area under the concentration–time curve during one dosing interval, area under the concentration–time curve from 0 to 24 hours, and half-life of idasanutlin (and M4 metabolite RO6802287)
- Total clearance and volume of distribution of cytarabine
- Effect of idasanutlin on cytarabine PK
- Effect of cytarabine on idasanutlin PK

The PK outcome measures will be investigated by the Roche Modeling and Simulation group. Results of the PK analyses will be reported in the population PK report.

### **2.2.6 Patient-Reported Outcome Measures**

The patient-reported outcome (PRO) measures for this study are as follows:

- European Organization for Research and Treatment of Cancer Quality of Life Questionnaire Core 30 (EORTC QLQ-C30)

- EuroQol 5-Dimension 5-Level (EQ-5D-5L) questionnaire

### 2.3 DETERMINATION OF SAMPLE SIZE

A mechanistic simulation model was used to determine sample size based on the following assumptions:

- Final analysis on OS in patients with *TP53* wild type (WT) using a 2-sided log-rank test at the 5% significance level
- 85% power to detect an OS HR (HR) of 0.67 for idasanutlin + cytarabine versus placebo + cytarabine in patients with *TP53* WT, corresponding to a 33% risk reduction of death, corresponding to an improvement in median OS from 6 months to 9 months (50%)
- Proportions of long-term survivors of 8.0% in the placebo + cytarabine treatment arm and 16.1% in the idasanutlin + cytarabine treatment arm

To compute the necessary number of events, OS times were simulated based on the following assumptions:

- All simulated OS times for patients not considered to be long-term survivors were exponentially distributed.
- Probability of being a CR in the placebo + cytarabine treatment arm was 0.16.
- Probability of being a CR in the idasanutlin + cytarabine treatment arm was 0.323, implying an odds ratio for CR of 2.5 for idasanutlin + cytarabine versus placebo + cytarabine.
- Probability for a CR to be a long-term survivor was 0.5 in either treatment arm.
- An annual dropout rate was 5%.

Based on these assumptions, approximately 275 OS events in patients with *TP53* WT are required to provide 85% power for the primary analysis. The minimum detectable OS HR in this study is 0.78, assuming 275 OS events and a significance level of 5%, which corresponds to a minimal detectable median improvement from 6 to 7.7 months assuming exponentiality.

All patients will be randomized in this study. Assuming 85% of patients will have *TP53* WT and 15% will have *TP53* mutant disease, approximately 440 patients will be enrolled over approximately 29 months, corresponding to an estimated number of 374 patients with *TP53* WT.

In Version 6 of the protocol, an interim analysis for efficacy on OS of *TP53* WT patients was added. The sample size assumptions above remain unchanged other than the recruitment time (now estimated as 41 months). The interim analysis will occur at an information-fraction of 80% providing a power of 83% for the final OS analysis (see section 4.11.3).

## 2.4 ANALYSIS TIMING

The final OS analysis will occur when approximately 275 OS events in patients with *TP53* WT have been observed. It is expected that this analysis will take place approximately 4 years after enrollment start (assuming 9 *TP53* WT patients enrolled per month).

A follow up (updated) OS analysis will be performed at the end of the study, expected approximately 5.5 years after enrollment start (2 years after the last patient is enrolled or after all patients have died, whichever occurs first).

A non-binding futility interim analysis will be performed by the independent data coordinating center (iDCC) and reviewed by the independent Data Monitoring Committee (iDMC). The futility interim analysis will be based on the confirmed CR response, which is defined in Section 4.4.2.

At the time of the study design, the timing of the futility and final analyses have been estimated assuming that on average 12 patients per month are enrolled for the first 15 months, followed by 18 patients per month for 14 months and 8 patients for the last month.

It was expected that the futility interim analysis will occur approximately 18 months after study start. Further details on the interim analyses, such as stopping rules and criteria, are provided in the iDMC charter and in section 4.11.

An interim OS analysis will occur at an information-fraction of 80% (see Section 4.11.3).

## 3. STUDY CONDUCT

### 3.1 RANDOMIZATION ISSUES

Approximately 440 patients will be enrolled in this 2:1 randomized trial, corresponding to a higher probability to be in the idasanutlin+cytarabine treatment arm (i.e., about 293 patients in the idasanutlin+cytarabine treatment arm and 147 patients in the placebo+cytarabine treatment arm).

Randomization will be performed through the interactive web response system (IWRS) using a stratified permuted block randomization scheme. The randomization stratification factors are as follows:

- Age (< 60 years vs. ≥ 60 years)
- Cytogenetic and molecular risk (favorable/intermediate vs. adverse) at initial diagnosis
- Prior response to initial anti-leukemic therapy (refractory vs. CR ≥ 90 days but ≤ 1 year vs. CR > 1 year)

- Prior HSCT versus no prior HSCT

Discordance between the IWRS and the electronic Case Report Form (eCRF) data will be summarized.

This is a double-blind study (i.e., neither the sponsor personnel, the patients, nor the treating physician will know the assigned treatment arm). However, the randomization code will be made available to the bioanalytical manager to facilitate the analysis of PK samples.

### **3.2 DATA MONITORING**

An iDMC will be used to assess patient safety and treatment efficacy at defined intervals. Specific details of the schedule of iDMC activities can be found in the iDMC charter.

The iDMC will first meet to assess the safety of the study after 30 patients have been enrolled and completed the first cycle with clinical response assessment available. Thereafter, the iDMC will have regular safety review meetings approximately every 3 months until the futility interim analysis. After this interim futility analysis, the iDMC will meet approximately every 6 months to assess the safety of the study. In addition, the iDMC will perform an interim efficacy analysis on OS at an information-fraction of 80% (see section 4.11.3). Both the Sponsor and the iDMC can request ad hoc iDMC meetings for any reason.

Following each meeting, the iDMC will recommend to the Sponsor whether the study should continue according to the protocol or may suggest changes to the protocol based on the outcome of data review.

At the futility interim analysis, the iDMC will also perform an ordinary safety review and a review of biomarker data. The iDMC will make recommendations on the following:

- Safety monitoring (including gastrointestinal toxicity and early death criteria)
- ECG monitoring
- Biomarker classification (see Section 4.5)

The details about the iDMC recommendation after the futility interim analysis are described in Section 4.11.1, each safety analysis in section 4.11.2 and the interim efficacy analysis in section 4.11.3.

The Sponsor will make the final decision for continuation or discontinuation of the study, or early unblinding, on the basis of the iDMC's recommendation (see Section 6.4 of the iDMC Charter).

## **4. STATISTICAL METHODS**

Except where specified otherwise, continuous data will be summarized with descriptive statistics (number of non-missing data, mean, standard deviation, median, minimum, and maximum). Categorical parameters data will be described using frequencies and percentages.

Descriptive summaries will be provided by treatment group. The main treatment comparison is between idasanutlin+cytarabine and placebo+cytarabine in *TP53* WT patients and all patients who have been randomized. All the statistical tests will be 2-sided.

### **4.1 ANALYSIS POPULATIONS**

#### **4.1.1 Randomized Population**

##### **4.1.1.1 *TP53* Wild type Intent-to-Treat Primary Population**

All randomized *TP53* WT patients will be included in the *TP53* intent-to-treat (*TP53* ITT) population. The *TP53* ITT population is the primary population for the analysis of the primary and secondary efficacy endpoints (see 4.4). Efficacy analyses will be done according to the randomized treatment arm regardless of which treatments the patients received.

Patients with wild-type *TP53* and *TP53* mutants with retained functionality will, together, form the *TP53* WT ITT primary population based on the variant types as described in [Appendix 2](#).

The futility interim analysis population will comprise the first 120 patients with *TP53* WT who were randomized, have received at least 80% of first treatment cycle (of the total planned dose of each study compound) and have data for response (including confirmed response for those with CR, CRp at end of Cycle 1) or who were withdrawn before time of response/confirmation.

##### **4.1.1.2 All-Patient Intent-to-Treat Population**

All randomized patients, that is, patients who are *TP53* WT or mutant or with a mutation status at screening unknown, will be included in the intent-to-treat (ITT) population. Efficacy analyses will be done according to the randomized treatment arm regardless of which treatments the patients received.

#### **4.1.2 Per Protocol Population**

A per protocol analysis population is not defined for this study. Major protocol deviations will be summarized by treatment arm.

### **4.1.3 Pharmacokinetic-Evaluable Population**

The PK-evaluable population includes all patients with PK data. PK analyses will be performed on the PK-evaluable population according to the treatment the patients received.

### **4.1.4 Safety Population**

The all-patient safety population will include all patients who received any amount of study drug (i.e., idasanutlin, placebo, or cytarabine) and the safety *TP53* WT population will include all patients with *TP53* WT and *TP53* mutants with retained functionality based on the variant types as described in [Appendix 2](#) who have received any amount of study drug. Patients will be analyzed according to the received treatment, that is, patients who received at least one dose of idasanutlin for whatever reason will be analyzed under the idasanutlin+cytarabine treatment arm. Patients who only received cytarabine and/or placebo will be analyzed under the placebo+cytarabine treatment arm.

## **4.2 ANALYSIS OF STUDY CONDUCT**

The following analyses of study conduct will be provided by treatment arm for all randomized patients unless specified differently:

- A summary of the randomized patients by treatment arm, center, and country
- A summary of the analysis populations
- A summary of the patient disposition, study treatment administration, and reasons for study treatment discontinuation
- A summary of observation time
- A summary of the major protocol deviations

## **4.3 ANALYSIS OF TREATMENT GROUP COMPARABILITY**

Descriptive summaries will be provided by treatment arm. These will include, but are not limited to, the following parameters:

- Stratification factors
  - Age (< 60 vs. ≥ 60 years)
  - Cytogenetic and molecular risk (favorable/intermediate vs. adverse)
  - Prior response to initial anti-leukemic therapy (refractory vs. CR ≥ 3 months but ≤ 1 year vs. CR > 1 year)
  - Prior HSCT versus no prior HSCT
- Demographic characteristics at baseline:
  - Gender
  - Age (years)
  - Race

Eastern Cooperative Oncology Group performance status

- AML disease characteristics at baseline
  - AML disease status at study entry (first relapse, second relapse, first refractory to induction, or second refractory to induction)
  - Number of prior treatment regimens
  - European LeukemiaNet Risk category at initial diagnosis
  - TP53* status
  - Type of previous HSCT (allogenic vs. autologous)

Should country policy prohibit the collection of race and/or age information, patients will appear in the missing category of summary tables.

#### **4.4 EFFICACY ANALYSIS**

The primary and secondary efficacy outcomes will be assessed for the *TP53* WT ITT population (primary population), as defined in Section 4.1.1.1.

##### **4.4.1 Primary Efficacy Endpoint**

The OS analysis will assess the null hypothesis of equality of OS distributions in the idasanutlin+cytarabine and placebo+cytarabine treatment arms in *TP53* WT patients:

$H_0: OS_{\text{idasanutlin+cytarabine}} = OS_{\text{placebo+cytarabine}}$  versus  $H_1: OS_{\text{idasanutlin+cytarabine}} \neq OS_{\text{placebo+cytarabine}}$

OS distributions will be compared between the treatment groups using a 2-sided stratified log-rank test at an overall significance  $\alpha$  level of maximum 4%. The stratification factors will be the randomization stratification factors: age (<60 years vs.  $\geq 60$  years), cytogenetic and molecular risk (favorable/intermediate vs. adverse), prior response to initial anti-leukemic therapy (refractory vs. CR  $\geq 3$  months but  $\leq 1$  year vs. CR > 1 year) and prior HSCT versus no prior HSCT. The IWRS data will be compared with the eCRF data for each patient. For cases where there is a difference between the IWRS and eCRF data, the stratification factors as entered in the eCRF will be used in the primary endpoint analysis.

The OS survival curves in each treatment arm will be estimated using Kaplan-Meier methodology and summarized using Kaplan-Meier plots. The treatment effect of idasanutlin+cytarabine versus placebo+cytarabine will be expressed as an HR using a stratified Cox proportional-hazard regression, including a 95% CI. In addition to the OS HR, 6-monthly OS probabilities and the estimated median OS in each arm (if reached) will be presented, including 95% CI.

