#### **6.4.1 Primary Efficacy Endpoint**

The primary efficacy endpoint, OS, is defined as the time from randomization to death due to any cause. OS for patients who have not died at the time of the analysis will be censored at the date last known alive.

*The primary OS analysis of the study will assess the null hypothesis of equality of OS functions in the idasanutlin in combination with cytarabine (MDM2-chemo) arm versus the cytarabine given with a placebo (chemo) arm in the TP53 WT population as follows:*

H0:  $OS_{MDM2-chemo} = OS_{chemo}$  versus H1:  $OS_{MDM2-chemo} \neq OS_{chemo}$

A formal treatment comparison will be made using a two-sided stratified log-rank test at a significance level *defined using the O'Brien-Fleming alpha-spending function with overall Type I error rate at 0.05 corresponding to available information (see Section 6.11.2)*. Stratification factors that will be used are the same as for randomization, that is, age (<60 versus  $\geq 60$  years), cytogenetic and molecular risk (*favorable/intermediate versus adverse*), prior response to initial anti-leukemic therapy (refractory versus CR  $\geq 3$  months but  $\leq 1$  year versus CR > 1 year) and prior HSCT versus no prior HSCT.

Survival curves in each treatment arm will be estimated using Kaplan–Meier estimates. The Kaplan–Meier estimates will provide a visual description of the survival curves and the difference across treatment arms. The treatment effect will be quantified via a hazard ratio, computed from a stratified Cox proportional-hazards regression, including a 95% CI. To further describe and quantify OS, estimated median OS per arm and 1-year and 2-year survival probabilities, all including 95% CI, will be given. The effect of prognostic factors on OS will be assessed in an exploratory analysis using Cox multivariate regression.

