#### **4.4.2            Secondary Efficacy Endpoints**

The fixed-sequence testing procedure will be used ([Westfall and Krishen 2001](#)) to adjust for multiple statistical testing of the primary and key secondary efficacy endpoints, thereby controlling the overall type I error rate at a 2-sided significance level of 5%.

The following secondary endpoints will be tested in the *TP53* WT population in the following order provided the null hypothesis of the OS primary endpoint is rejected:

1. CR rate

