#### **4.11.3 Efficacy Interim Analysis**

At the time of the efficacy interim analysis (on OS) that will be conducted when 80% of the events have occurred (i.e., approximately 220 events), it is

anticipated that all patients have been enrolled. OS will be tested at the significance level determined using the O'Brien-Fleming alpha-spending function so the overall Type I error rate will be maintained at the 0.05 level. With 80% information, the alpha spending is 0.024.

The iDMC may recommend unblinding the study for efficacy if there is a significant difference in OS in favor of the experimental arm (alpha level 0.024 or as assessed based on actual number of OS events).

Accompanying this interim efficacy analysis, a non-binding additional futility assessment will be performed and the iDMC may recommend stopping the study for futility if the hazard ratio on overall survival is greater than or equal to one.

Further details about the interim analyses will be described in the iDMC Charter.

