### Efficacy

*An interim analysis for efficacy on OS is planned to be conducted by iDMC. The efficacy interim analysis will be conducted when 80% of the OS events have occurred (i.e., approximately 220 events). At this time, it is anticipated that all patients will have been enrolled.*

*For the interim efficacy analysis of OS, the significance level will be determined using the O'Brien-Fleming alpha-spending function with overall type I error rate at 0.05 level. At the time of the interim efficacy analysis, it is expected that 80% of the OS events will have occurred, corresponding to an alpha spending of 0.025 for the interim and 0.043 for the final OS analysis leading to a power of 83% for the final analysis.*

*The iDMC will test OS for efficacy and check if there is a significant difference (alpha level 0.025 or as assessed based on actual number of OS events) in OS in favor of the experimental arm.*

*Accompanying this interim efficacy analysis, a non-binding additional futility assessment will be performed and the iDMC may recommend stopping the study for futility if the hazard ratio on overall survival is greater than or equal to one.*

*Further details of the interim analyses will be described in the iDMC Charter and Statistical Analysis Plan.*

## Appendix 2

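### SAP 4.4.1 tests overall survival at an overall level of at most 4%, against the two-sided 5% with O'Brien-Fleming spending (0.043 at the final look) set everywhere else

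*SAP*

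**What the plan says.** SAP 4.4.1 compares the arms on OS with a "2-sided stratified log-rank test" at an overall significance "level of maximum 4"%. It does not say where 4% comes from or what happens to the remaining 1%.

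The other statements of the error rate are these:

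- Protocol 6.4.1: the level is "defined using the O'Brien-Fleming alpha-spending function with overall Type I error rate at 0.05 corresponding to available information". The synopsis appended to the SAP repeats this.
- Protocol 6.11.2, and the same synopsis: 80% of the OS events at the interim, "corresponding to an alpha spending of 0.025 for the interim and 0.043 for the final OS analysis".
- SAP 4.4.2: a fixed sequence over the primary and key secondary endpoints, "controlling the overall type I error rate at a 2-sided significance level of 5"%.
- SAP 4.11.3: O'Brien-Fleming spending "so the overall Type I error rate will be maintained at the 0.05 level", with 0.024 at the interim or the value implied by the actual number of deaths.
- SAP 2.3, among the sizing assumptions: the final OS analysis "using a 2-sided log-rank test at the 5% significance level".

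Sections 2 to 4 of the SAP never print the final level of 0.043. In the SAP it appears only in the synopsis copied as Appendix 1.

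**The concern.** An overall error rate of 4% and an overall error rate of 5% cannot both hold for the same test. The conflict sits in the section that defines the primary analysis, where a programmer or assessor looks first.

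Someone working only from SAP sections 2 to 4 finds two candidate levels for the final look, 4% in 4.4.1 and 5% in 2.3. Neither is the level that the spending rule produces. A p-value between the competing thresholds would be a success under one document and a failure under the other, and the choice between them would be made after unblinding. Rejection of the OS hypothesis also opens the 11 ordered secondary tests in SAP 4.4.2, so the dispute would carry into all of them.

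**Working it through.** **Inputs.** Overall two-sided alpha 0.05 (protocol 6.4.1; SAP 4.4.2 and 4.11.3). Interim at 220 of 275 deaths, so t = 220/275 = 0.80 (protocol 6.11.2; SAP 4.11.3). Allocation 2:1 (SAP 2). Power 85% at 5% before the interim was added (SAP 2.3).

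**1. Reproduce the printed levels under 5% overall.** With 2.5% per side, the two-sided amount spent at the interim is

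4 × [1 − Φ(z₀.₉₈₇₅ / √t)] = 4 × [1 − Φ(2.2414 / √0.80)] = 4 × [1 − Φ(2.506)] = 0.0244.

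The final critical value c solves P(Z₁ ≥ 2.250 or Z₂ ≥ c) = 0.025, where Z₁ and Z₂ are bivariate normal with correlation √0.80. This gives c = 2.025, a nominal two-sided level of 0.0429. These match 0.024 in SAP 4.11.3 and 0.043 in protocol 6.11.2. The classical O'Brien-Fleming boundary gives 0.0238 and 0.0432, so the final level rounds to 0.043 either way.

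**2. Take 4% literally as the overall level.** The same method with 2% per side gives 0.0186 at the interim and 0.0345 at the final look. Neither figure is printed, and 0.0186 contradicts the SAP's own 0.024.

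**3. Take 4% as the final nominal level.** From the same bivariate normal, 0.024 then 0.040 gives a total two-sided type I error of 0.0474. That stays below 5%, but it is not an overall 4%, and 0.040 is not 0.043.

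**4. Look for a spending form that yields 4%.** Applying the formula directly to two-sided 5%, 2 × [1 − Φ(1.960/√0.80)], gives 0.0284 and then 0.0402. The final level is close to 4%, but the interim level fits neither 0.024 nor 0.025.

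**5. Use the 5% of SAP 2.3 at the final look.** 0.024 then 0.050 gives a total of 0.0559, above the 5% that SAP 4.4.2 and 4.11.3 promise.

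**6. Consequences.** The critical hazard ratio at 275 deaths is exp(−z / √(275 × 2/9)) = exp(−z / 7.817).

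| Final two-sided level | Critical hazard ratio |
|---|---|
| 0.050 | 0.778 |
| 0.043 | 0.772 |
| 0.040 | 0.769 |
| 0.0345 | 0.763 |

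The first row reproduces the 0.78 in SAP 2.3.

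For power, set the drift to give 85% at a single 5% look: 1.960 + 1.036 = 2.996. Total power is then 84.3% with 0.0244 and 0.0429, and 83.7% with 0.024 and 0.040. The probability of not rejecting at the interim and ending with p between 0.040 and 0.0429 is 0.6%, or 1.8% of trials that reach the final look. If 4% is taken literally as overall, the disputed range widens to 0.0345 to 0.0429, with probability 1.9%.

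**The case against.** The strongest reply is that this is a labelling slip with little consequence. The spending rule is prespecified in protocol 6.4.1 and 6.11.2 and in SAP 4.11.3. The levels are recomputed from the actual deaths, so 0.043 is itself only a planned figure. The rationale for SAP Version 3 lists no change to the overall alpha, so 4% is probably 0.043 rounded and mislabelled. Both readings of 4% are conservative, and the power cost with 4% as the final level is 0.6 percentage points. These points stand and limit the size of the problem. The rounding explanation remains an inference. SAP section 1 says that departures from the protocol will be set out in the SAP, so 4% could also be read as a deliberate change.

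The second reply concerns SAP 2.3. There, 5% is an input to the original sizing. The same section goes on to describe the added interim, gives 83% power for the final analysis and points to 4.11.3. The same sizing sentence also stands in protocol 6.1 and the synopses. That is fair: a careful reader would not use 5% at the final look, and 0.0559 applies only if someone does. The sentence needs a clarification and is not evidence of an inflated design.

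Third, the printed interim level also differs (0.025 in the protocol, 0.024 in the SAP). Pairing 0.025 with 0.043 gives a total of 0.0504. But the rule gives 0.0244 at 220 deaths, 0.0248 at 221 and 0.0252 at 222, so this difference is close to rounding and both documents recompute the value. No such allowance explains an overall 4%.

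**Conclusion.** The concern holds. SAP 4.4.1 states an overall level for the primary test that contradicts the protocol and the rest of the SAP, and no reading of 4% reconciles it with the printed 0.024 and 0.043. The design itself is sound: overall two-sided 5% with O'Brien-Fleming-type spending reproduces the planned levels.

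The practical effect is small and, for 4%, conservative. It still needs correcting because a Phase III primary endpoint should have a single success threshold, fixed before OS is unblinded.

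The level calculations assume exactly 220 and 275 deaths and the per-side form of the spending function, which the printed values support. The power and window figures are approximations: they use a proportional-hazards normal drift calibrated to 85%, whereas the documents sized the trial by simulation with long-term survivors.

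**What to change.** In SAP 4.4.1, replace the 4% wording with: overall two-sided significance level 5% (2.5% per side), O'Brien-Fleming-type alpha spending, planned nominal two-sided levels 0.0244 at 220 deaths and 0.0429 at 275 deaths, both recomputed from the actual death counts.

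In SAP 2.3, add that 5% is the overall level and not the nominal level of the final look.

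Optionally, at the next amendment, print one interim value in SAP 4.11.3, protocol 6.11.2 and the synopses, and carry the 2.3 clarification into the matching sizing sentence in protocol 6.1 and the synopses.

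The cost is two SAP sentences, made before the OS interim is unblinded. No protocol amendment is needed now, and no additional patients or analyses.
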